9.0 Consent Process

Signed informed consent will be obtained from study participants. The consent process will take place via one of the following modalities: 1) Remote or in person electronic consent (e-consent) via REDCap (if remote, e-consent will be facilitated with a discussion over the phone or via video), 2) Remote consent via doxy.me facilitated with either a discussion over the phone or video connection via doxy.me, 3) Mailed (paper) consent facilitated with a discussion over the phone, or 4) in person consent (e.g., in clinic).

All participants will be provided with a hard copy and/or an electronic copy of the consent form. Participants will be informed that participation in this research is strictly voluntary. Informed consent will include a detailed description of the purpose and the procedure of the study emphasizing our policy regarding privacy and confidentiality and an opportunity for the individual to ask any questions or voice concerns. Signatures on the consent form may be obtained with paper and pen OR electronically via REDCap/doxy.me. Participants who do not have access to the required technology to complete consent remotely via REDCap or doxy.me will be given the option to complete consent via mail facilitated with a

discussion over the phone. For participants consented via doxy.me, we will track software analytics anonymously, while using the platform, for potential future secondary data analysis examining usability of remote electronic consent. We have discussed this with doxy.me developers, who have assured us that we can get this data for a given protocol in an anonymous way. We are only interested in times it takes individuals to accomplish given tasks within doxy.me. For example, track the time it takes them to navigate through the online document and time it takes them to sign the consent form electronically.

10.0 Study Design / Methods

Usability Testing

Following initial development of the modified e-visit, we will complete usability testing of the e-visit with 5 patients (up to 10 to account for attrition). Usability testing participants will complete all study procedures as outlined below for the pilot RCT, but will also be asked to provide additional feedback as they complete the e-visits so that the investigative team can iteratively refine and improve the e-visits. Inclusion/exclusion criteria for usability testing participants will be the same as criteria for pilot RCT participants (see section 5.0 above). As participants complete the e-visits remotely, research staff will be connected in real time to the participant via audio and/or video. As participants complete the e-visits, we will follow the Concurrent Think Aloud method to elicit real-time feedback and research staff will take notes on emotional reactions, task completion, task time, and errors¹¹. The compensation schedule for participants included in initial usability testing will be the same as for participants enrolled in the RCT. Following usability testing, [name] will then prioritize refinements which will be implemented by the BMIC Epic development team in preparation for the subsequent pilot trial.

Pilot RCT

A two-arm pilot RCT (N=100, up to 120 assuming 20% attrition) will test cessation treatment utilization, smoking cessation outcomes, and COPD diagnosis rates as a function of smoking cessation e-visit vs. TAU. Recruitment will primarily occur proactively and remotely via the EMR. We will conduct an automated EMR search via established procedures for all patients treated within MUSC DFM clinics during the past 12 months who: 1) smoke, 2) are ≥ 40 , 3) have MyChart accounts, and 4) do not have COPD on their problem list. **These patients will be sent a MyChart message from a member of their care team inviting them to participate in a research study for cigarette smokers. These messages will only be sent to patients of PCPs who have agreed that their patients may be contacted for the purpose of this study. This invitation will include clear opt out procedures should the patient not wish to be contacted in the future for the purpose of this study. Clinical providers included in the Usability Testing phase of the project will not be asked to directly refer their own patients to the study. However, their patients may still be recruited via the EMR.** After sending these automated e-mail messages via MyChart, the study team may also call, e-mail, and/or text message potential participants to notify them that a message was sent to them via MyChart. Again, such contact will only be made to patients of PCPs who have agreed that their patients may be contacted for the purpose of this study. If interested, participants will complete a screening online via MyChart to determine study eligibility (see above for inclusion criteria). After completing determination of eligibility, if eligible and interested in participating in the study, participants will be scheduled for a time to complete informed consent (see 9.0 Consent Process). After consent is obtained, participants will be randomized 2:1 to receive either the smoking cessation e-visit or TAU. If randomized to the e-visit condition, participants will be sent a link to initiate the e-visit. All e-visit medication recommendations will be reviewed by physicians included on this IRB protocol. Medications will be e-prescribed to a mail order pharmacy (e.g., MUSC's mail order pharmacy) and then mailed to participants, with all costs covered by the study. Note

that only FDA approved cessation medications will be recommended, which include nicotine replacement therapy (patch, gum, lozenge), varenicline, or bupropion. Medications will only be recommended if a participant does not have a contraindication for that medication. Women who indicate during the e-visit that they are currently pregnant or are planning to become pregnant within the next 6 months will not receive a medication recommendation/prescription as a result of the e-visit. These women will receive a counseling referral. Any woman under the age of 55 who receives a varenicline recommendation as a result of the e-visit will subsequently be asked within the e-visit if she is willing to complete a pregnancy test that will be mailed to her at no cost to verify that she is not pregnant prior to taking varenicline.

Women under the age of 55 who respond “Yes” to this item will be mailed a pregnancy test by study staff and will be required to verify (with signature) that they completed the test and are not pregnant via REDCap. Women under the age of 55 who respond “No” to this item will not receive varenicline as a result of the e-visit. These women instead will either receive NRT, bupropion and/or counseling based on other contraindications and medication preferences indicated throughout the e-visit. Participants will be scheduled for a follow-up e-visit one month following their initial e-visits. The follow-up e-visit may also result in a medication recommendation that will be e-prescribed and mailed to the participant as outlined above for the baseline e-visit. If randomized to the TAU condition, participants will be provided information on quitting smoking, including information about the state quitline, and will be provided a recommendation to contact their PCP to schedule a medical visit to discuss quitting smoking.

For participants randomized to the e-visit condition, the baseline e-visit will include a 5-item questionnaire (the CAPTURE) to assess COPD symptoms. Participants who score ≥ 2 on this measure will be invited to complete home spirometry. These participants will be mailed a home spirometer and will be invited to complete an additional e-visit after receiving the home spirometer at which time they will be instructed regarding how to use the device and will upload a video of themselves completing home spirometry. Participants will also be asked to enter into the e-visit metrics available via the spirometer including FEV1 and peak expiratory flow. These videos will be reviewed by a study attending physician and follow-up care will be provided consistent with best clinical practices. In addition to home spirometry, all patients who screen positive on the CAPTURE during the baseline e-visit will be referred to an in person appointment for spirometry/bronchodilation consistent with best practices. Costs related to in person spirometry testing will be paid for by the study for appointments completed by the time of the 3-month assessment. Although the medical order for spirometry testing may remain active following the 3-month assessment, any testing completed after the date of the 3-month assessment will not be paid for by the study.

All participants will subsequently be text messaged and/or emailed a REDCap link, accessible via smartphone, tablet, or computer to complete study assessments. These assessments will occur at baseline (following consent), 1-month following study enrollment, and 3-months following study enrollment. Assessments are estimated at 20 minutes each and will be administered remotely via REDCap through our established procedures. Participants will be compensated via electronic gift cards (e.g., Amazon) which will be emailed or texted to participants. Participants will receive \$30 for completion of the baseline assessment questionnaire. After completing each follow-up questionnaire within 72 hours of being emailed the link, participants will be compensated \$30. Participants will be compensated \$30 for each completed carbon monoxide recording. They will be compensated an additional \$100 for completion of all three sets of questionnaires and both carbon monoxide samples. E-visit acceptability and feasibility will be assessed both by examining the percentage of patients who complete the initial and follow-up e-visits, and by participant self-report during follow-up assessments. Participants will respond to items assessing ease of use, satisfaction, and pros/cons of the e-visit. Analytics data (e.g., amount of time it takes to complete the e-visit, amount of time it takes the provider to review the e-visit) will also be collected as will data on provider fidelity to e-visit recommendations (captured by reviewing within Epic

whether the provider administered treatment consistent with e-visit recommendations). Cigarette smoking, use of other tobacco products (e.g., e-cigarettes), and quit attempts/quit duration will be assessed at each follow-up using a timeline followback for the last 6-months at baseline and since prior follow-up for each subsequent assessment^{7,8}. Nicotine dependence will be assessed at baseline via the Fagerstrom Test of Nicotine Dependence⁹. Participants will report motivation to quit and confidence in quitting using a modified Contemplation Ladder¹⁰. Expired air carbon monoxide will also be captured. Treatment utilization will be assessed via participant self-report. At each follow-up assessment, participants in both groups will be queried for: 1) use of a smoking cessation medication since the last assessment, 2) how the medication was obtained (e.g., via the study or another outlet such as MUSC's existing smoking cessation service), and 3) receipt of the 5As from their PCP⁶. COPD diagnosis will be assessed via participant self-report and via medical records review. At each follow-up time point, participants will be asked whether a clinical provider has given them a COPD diagnosis. Medical records will be reviewed for up to 12-months following completion of the 3-month follow-up survey to identify: 1) whether the participant was referred for in person spirometry, 2) whether the participant attended that appointment, and 3) whether the participant was given a diagnosis of COPD.

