1.0 Objectives / Specific Aims

The goal of this work is to develop, refine, and pilot test an electronic visit (e-visit) to: 1) deliver smoking cessation treatment to adults at risk for COPD and 2) to improve rates of COPD early detection and accurate diagnosis. We will conduct a pilot RCT (N=100, up to 120 assuming 20% attrition) of the COPD/smoking cessation e-visit as compared to treatment as usual (TAU), with primary objective to provide effect size estimates for a larger RCT. Specific aims are twofold:

Aim 1: Conduct usability testing of the smoking cessation/COPD e-visit with patients (N=5, up to 10 to account for attrition) followed by iterative refinements consistent with participant feedback.

Aim 2: Conduct a pilot, small-scale randomized controlled trial to examine COPD and smoking cessation outcomes associated with the E-Visit as compared to treatment as usual (TAU; i.e., no e-visit). Outcomes will include those related to: e-visit feasibility (i.e., time to complete e-visit, time for provider to review e-visit, % completed e-visits, qualitative feedback), COPD (early diagnosis rates as a function of treatment condition, emergency department visits for respiratory infection), smoking cessation outcomes (self-reported quit attempts/quit duration and biochemically verified cessation via carbon monoxide), and cessation medication utilization.

We hypothesize that participants randomized to the e-visit condition as compared to those randomized to the TAU condition will have higher (numerically, if not statistically significant) rates of COPD early diagnosis, cessation treatment utilization (medications, counseling), and superior cessation-related outcomes.

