6.0 Number of Subjects

We will recruit up to 10 patients for usability testing and 120 subjects for the pilot RCT.

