11.0 Data Analysis and Data Management

Data Analysis

As this is a pilot trial, our primary goal is to estimate an intervention effect size and our secondary goal is to examine the feasibility/acceptability of the e-visit. Precise parameter estimation can be achieved with 25-30 participants per group¹². To estimate an effect size for the smoking cessation e-visit intervention, we will randomize participants 2:1 (active:control), with 67 participants in the active condition and 33 in the control condition. Primary smoking-related outcomes for this trial include cessation treatment utilization (e.g., medication) and quit attempts. Assuming a cessation treatment utilization rate of 48% in the active condition and 11% in the control condition, with 2:1 randomization we will have 95% power to detect an effect. For quit attempts, assuming a quit attempt rate of 24% in the e-visit condition and 6% in the TAU condition, we will have 60% power to detect an effect. Our intent here is not a fully powered trial for cessation, but is rather to collect preliminary data to inform future trials.

Data analysis for the primary objective will focus on descriptive analysis of primary smoking-related outcomes. Descriptive statistics (e.g., frequencies, percentages) will be calculated for the primary smoking-related outcomes (treatment utilization, quit attempts). Because rates of these primary outcomes are expected to be low in control group, we will utilize Fisher's exact tests to compare rates between the e-visit and TAU groups. Secondary exploratory analyses for this primary objective will examine changes in these outcomes over time by treatment condition. We will utilize Generalized Estimating Equations (GEEs) with log link functions, which will allow us to account for correlated repeated measures within study participants. Planned covariates include sex and the main effect of time.

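### The attrition allowance does not reconcile: 120 less 20% leaves 96, not 100, and Section 11 puts the number randomised at 100 while Section 6 recruits 120

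*Combined protocol and SAP*

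**What the plan says.** The sample size appears in four places.

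- Section 1.0 (Objectives / Specific Aims): "We will conduct a pilot RCT (N=100, up to 120 assuming 20% attrition"). Section 10.0 (Pilot RCT) repeats it: "A two-arm pilot RCT (N=100, up to 120 assuming 20% attrition").
- Section 6.0 (Number of Subjects): "We will recruit up to 10 patients for usability testing and 120 subjects for the pilot RCT".
- Section 10.0, on timing: "After consent is obtained, participants will be randomized 2:1 to receive either the smoking cessation e-visit or TAU". Section 13.0 (Protections Against Risk) gives the same order: consent, randomisation, baseline assessments, intervention.
- Section 11.0 (Data Analysis): "we will randomize participants 2:1 (active:control), with 67 participants in the active condition and 33 in the control condition".

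Section 11.0 gives two power figures. For treatment utilisation at 48% against 11%, "with 2:1 randomization we will have 95% power to detect an effect". For quit attempts at 24% against 6%, "we will have 60% power to detect an effect". It names Fisher's exact test for the comparison of rates. It states no alpha, does not say how power was calculated, and mentions neither attrition nor 120. Its general size criterion is "Precise parameter estimation can be achieved with 25-30 participants per group". It adds that the trial is not meant to be fully powered for cessation.

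**The concern.** There are two inconsistencies, and a gap that follows from them.

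First, an allowance for 20% attrition should divide the target by 0.8. The plan multiplies it by 1.2, so the stated ceiling does not deliver the stated target at the stated attrition rate.

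Second, Section 11.0 calls 67/33 the numbers randomised, but Section 6.0 recruits 120 for the RCT and randomisation follows consent directly. Either 67/33 is the number expected to remain and has been mislabelled, or 100 are randomised and the ceiling of 120 has no role.

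The gap is that the two power figures have no identifiable denominator. The trial's main purpose is to supply effect size estimates for a larger RCT, so a reader needs to know how many participants those estimates will rest on and what the quoted power describes.

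**Working it through.** **Inputs.** Target 100, ceiling 120 and attrition 20% (Sections 1.0 and 10.0); 2:1 allocation, 67/33, rates 48% v 11% and 24% v 6%, Fisher's exact test (Section 11.0). **Assumptions:** two-sided alpha 0.05, because none is stated; only those with follow-up are analysed; the plan's rates hold in them.

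**1. The attrition allowance.**
- The plan's 120 is reproduced only as 100 × (1 + 0.20) = 120.
- Size needed to keep 100: 100/(1 − 0.20) = 125.
- Retained from 120: 120 × 0.80 = 96. By arm, 80 × 0.80 = 64 and 40 × 0.80 = 32.
- Going from 120 to 100 is a loss of 20/120 = 16.7%, not 20%.

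**2. If 67/33 are randomised, as Section 11.0 says.** 67 × 0.80 = 53.6 and 33 × 0.80 = 26.4, total 80. In whole participants this is 53/27 or 54/26.

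**3. Power of the planned test.** Power is the sum, over all pairs of counts (x, y), of Bin(x; n1, p1) × Bin(y; n2, p2) where the two-sided Fisher p-value is at most 0.05.

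| Number analysed | Quit attempts, 24% v 6% (plan: 60%) | Utilisation, 48% v 11% (plan: 95%) |
|---|---|---|
| 67/33 | 60.1% | 97.7% |
| 64/32 (120 randomised, 20% lost) | 58.3% | 97.0% |
| 53/27 (100 randomised, 20% lost) | 43.3% | 93.2% |
| 54/26 (same, rounded the other way) | 46.2% | 92.9% |
| 80/40 (120 randomised, none lost) | 70.1% | 99.3% |

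Fisher at 67/33 reproduces the stated 60% but not the stated 95%.

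**4. Do the stated figures identify a sample size?** Two other standard calculations were tried at attrition-reduced sizes.
- Arcsine approximation at 54/26: power = Φ(h√(n1n2/(n1+n2)) − 1.96), with h = 2·asin√p1 − 2·asin√p2 and √(54 × 26/80) = 4.189. Quit attempts: h = 0.529, Φ(2.216 − 1.960) = 60.1%. Utilisation: h = 0.855, Φ(3.580 − 1.960) = 94.7%. Both stated figures are matched.
- Pooled normal approximation at 64/32, quit attempts: pooled rate (64 × 0.24 + 32 × 0.06)/96 = 0.18; null SE 0.0832, alternative SE 0.0679; Φ((0.18 − 1.96 × 0.0832)/0.0679) = 59.9%.

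So about 60% comes out at 67/33, 64/32 or 54/26, depending on the method.

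**5. Precision.** The 95% half-width for the risk difference is 1.96 × √(p1q1/n1 + p2q2/n2). At 67/33, 64/32 and 53/27 it is 13.0, 13.3 and 14.6 points for quit attempts, and 16.0, 16.4 and 17.9 points for utilisation.

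**The case against.** The strongest reply is that the sections, read together, make 120 the enrolment ceiling and 100 the working target. The shortfall is then four retained participants and about 2 points of power, in a pilot that is about estimation and disclaims full power for cessation. The 32 retained controls exceed the 25–30 per group on which the plan relies, and no test or decision rule changes. All of that stands, and it is why the point is minor. It does not remove the need to correct Section 11.0, which says in terms that 67/33 are randomised.

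A reader might go further and infer that the power figures ignore attrition, because Fisher at 67/33 returns 60.1%. The documents do not support that. The same calculation gives 97.7% for utilisation, not 95%, while an arcsine calculation at 54/26 returns 60.1% and 94.7%. The plan names Fisher for the analysis but not for the power calculation. Nothing shows that arcsine was used either; the question cannot be settled from the text.

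It might also be said that missing outcomes could be counted as failures, so that the numbers randomised and analysed coincide. No such rule is stated. If there were one, and the assumed rates held in everyone randomised, 120 randomised would give about 70% for quit attempts, so the number would still have to be reconciled.

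**Conclusion.** Two things are certain and need no assumption about test, alpha or missing data: 120 with 20% attrition leaves 96 (64/32), not 100, and Section 11.0's 100 randomised conflicts with the 120 recruited in Section 6.0. It is also plain that the plan leaves the sample size, method and alpha behind its 95% and 60% unstated. Whether attrition was allowed for in those figures cannot be shown either way.

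The size depends on which number is meant. If 120 are randomised, the planned Fisher test has about 58% power for quit attempts and 97% for utilisation. If 100 are randomised, it has about 43–46% and 93%. These values rest on the assumptions listed in the working. The lower pair should not be read as the stated figures with attrition taken out, because the authors may have used a different method.

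Severity is minor. The 26 or 27 controls retained in the less favourable case still lie within 25–30 per group. This corrects stated figures and does not challenge the design.

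**What to change.** Text changes only:

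1. Decide whether 120 (80/40) or 100 (67/33) are randomised, and use that number in Sections 1.0, 6.0, 10.0 and 11.0.
2. Give the expected number with follow-up at 20% attrition: about 96 (64/32) from 120, or about 80 (53/27 or 54/26) from 100. Label each pair of arm sizes as randomised or as expected with follow-up.
3. In Section 11.0, state power for the planned Fisher test at the expected follow-up size, with its alpha and sidedness, and say that it counts only those with follow-up. At two-sided 0.05 this is about 58% (quit attempts) and 97% (utilisation) at 64/32, or about 43–46% and 93% at 53/27 or 54/26. If the authors prefer to keep 95% and 60%, they should state the size, method and alpha that produce them.

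The cost is a quit-attempt power that looks slightly less favourable if 120 are randomised, and clearly less so if only 100 are. No participants are added and no planned test changes. Keeping 100 after 20% attrition would instead mean a ceiling of 125 (about 83/42), five more than now, which the 25–30 per group criterion does not require.

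### The exploratory GEE of change over time uses outcomes recalled over windows of unequal length, with no common interval or offset, so its time coefficient partly measures window length

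*Combined protocol and SAP*

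**What the plan says.** Section 10.0 schedules assessments at baseline, "1-month following study enrollment, and 3-months following study enrollment". Smoking, other tobacco use and quit attempts are collected "using a timeline followback for the last 6-months at baseline and since prior follow-up for each subsequent assessment"; Section 4.0 says the same. Treatment utilization is handled differently: at each follow-up, participants report "use of a smoking cessation medication since the last assessment". No baseline recall period is given for it.

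Section 11.0 names treatment utilization and quit attempts as the primary smoking-related outcomes. The arms are compared descriptively and with Fisher's exact tests, chosen because low rates are expected in the control group. Then: "Secondary exploratory analyses for this primary objective will examine changes in these outcomes over time by treatment condition". The method is "Generalized Estimating Equations (GEEs) with log link functions", to allow for repeated measures within participants. On model terms the plan says: "Planned covariates include sex and the main effect of time".

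The plan does not state:
- whether the repeated outcome is a yes/no, a count or a rate;
- whether baseline enters as an outcome;
- any offset or common interval;
- an arm-by-time term;
- what happens if a cell has no events.

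**The concern.** A longer recall window captures more events even when behaviour does not change. For quit attempts the windows are about 6, 1 and 2 months; for medication use they are about 1 and 2 months. A model that treats these as successive values of one outcome attributes the difference in window length to time. Change over time is the purpose of this analysis, so the affected coefficient is the one it exists to estimate. The pilot is meant to supply estimates for a larger trial, and an apparent rise or fall in quit attempts could be carried into that design as though it were real.

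**Working it through.** **Inputs.** Section 11.0: 24% (e-visit) and 6% (TAU) for quit attempts, "with 67 participants in the active condition and 33 in the control condition". Section 10.0: assessments at 0, 1 and 3 months. The period covered by the 24% and 6% is not stated.

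**1. The plan's own figure.** The text reads "assuming a quit attempt rate of 24% in the e-visit condition and 6% in the TAU condition, we will have 60% power". Exact enumeration of a two-sided Fisher's exact test at alpha 0.05 (alpha and sidedness assumed) with 67 and 33 gives 60.1%, so the stated power is reproduced. It describes a single comparison of two proportions. It does not bear on the GEE and does not show which window the rates cover.

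**2. Effect of window length on quit attempts.** Assume a constant hazard and that the planned rates cover 3 months. The proportion with an event in a window of w months is then 1 − (1 − p)^(w/3).

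| Window | TAU, p = 0.06 | E-visit, p = 0.24 |
|---|---|---|
| 1 month (first follow-up) | 1 − 0.94^(1/3) = 2.0% | 1 − 0.76^(1/3) = 8.7% |
| 2 months (second follow-up) | 1 − 0.94^(2/3) = 4.0% | 1 − 0.76^(2/3) = 16.7% |
| Ratio, second to first | 1.98 | 1.91 |

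The true rate is constant, yet the outcome roughly doubles in both arms. This does not depend on how baseline is used.

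**3. If baseline is also a time point.** At the TAU rate, a 6-month window gives 1 − 0.94² = 11.6%. The first follow-up is then 2.04/11.64 = 0.175 of baseline and the second 4.04/11.64 = 0.347, where both ratios should be 1. A GEE simulation (log link, Poisson variance, categorical time, arm and time main effects, independent windows) with no change and no arm effect agreed. In the 179 of 200 runs fitted, the median time ratios were 0.18 and 0.33, nominally significant in 72% and 50%.

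**4. Arm contrast within a window.** Both arms share each window. The risk ratio is 8.74/2.04 = 4.28 in the 1-month window and 16.72/4.04 = 4.14 in the 2-month window, against 24/6 = 4.00 over 3 months. The contrast barely moves.

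**5. Pooling baseline with follow-up.** With the planned rates as the true effect after baseline and equal arms at baseline, the simulated main-effects model gave a median arm ratio of 2.15, against about 4.2 at follow-up. This arises only if baseline is an outcome and no arm-by-time term is fitted. The plan states neither, but it shows why both should be settled.

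**6. Empty TAU cells for quit attempts, n = 33.**
- If 6% covers 3 months: 0.9796^33 = 51% at the first follow-up and 0.9596^33 = 26% at the second.
- If 6% applies to each visit: 0.94^33 = 13% at each.

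These matter for a model with an arm-by-time term. With main effects only and follow-ups only, the arm ratio fails to be finite only if TAU has no event at either visit: 0.94^33 = 13% on the first reading, or 0.94^66 = 1.7% on the second, taking visits as independent.

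**7. Medication use.** The same formula could be applied to 48% and 11%, but a constant hazard is doubtful here. Medication is mailed after the baseline e-visit and possibly again after the one-month e-visit, so use may be front-loaded and may continue across both windows. Only the unequal window length (about 1 and 2 months) is relied on.

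**The case against.** The strongest reply is that the plan is silent rather than wrong. It does not say that raw per-assessment outcomes will be modelled, and timeline followback data can be re-cut to a common interval. The analysis is labelled secondary and exploratory; the Fisher's exact tests and the feasibility criteria do not use it. All of this is fair and limits the consequence. But the stated measurement windows and the stated analysis, followed as written, lead to a biased time trend, and nothing in the text directs the analyst to re-cut the data.

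A reader might infer more than the documents support:

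- *That the model cannot show change by arm.* The aim names treatment condition, and the covariate sentence uses the word *include*. Arm itself is not listed either, so the list can hardly be exhaustive. The arm-by-time term is unlisted, not excluded.
- *That medication use also has a 6-month baseline window.* That recall belongs to the timeline followback; utilization is asked at follow-ups only.
- *That empty TAU cells are to be expected.* The 51% and 26% need both an interaction model and a 3-month reading of the 6%, which the plan does not give.

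**Conclusion.** The point holds for the time trend in a secondary exploratory analysis. If per-assessment outcomes are modelled, quit attempts show a spurious rise of about 1.9- to 2.0-fold between follow-ups. If baseline is a time point, TAU shows a spurious fall from 11.6% to 2.0%. These sizes assume a constant hazard and planned rates that cover 3 months; the direction of the bias needs only that longer windows catch more events. For medication use the time effect is likewise uninterpretable as change, but no reliable size can be given.

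It would be wrong to conclude that the trial's effect estimates are compromised. Same-window arm contrasts (4.28 and 4.14) and the Fisher's exact tests are not materially affected. The missing arm-by-time term, role of baseline and empty-cell rule are gaps in specification to close at the same time.

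**What to change.** Amend the analysis section before the data are analysed:

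1. **Quit attempts.** Derive them from the timeline followback in equal 30-day intervals (days 1–30, 31–60, 61–90) and use these as the repeated outcome. This assumes the instrument is kept in its dated calendar form.
2. **Baseline.** Use the 6-month baseline quit-attempt value as a covariate, not a time point.
3. **Model terms.** List arm, categorical time, arm-by-time and sex.
4. **Medication use.** Report arm contrasts within each window and do not interpret the time main effect as change. An offset for days since the last assessment is not advised, because it builds in a doubtful constant hazard.
5. **Empty cells.** If an arm-by-visit cell has no events, report the risk difference with an exact or score interval for that visit.

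The cost is revised wording and slightly more programming, with no new data collection. The interaction estimate will be imprecise with 33 TAU participants and should be reported as such.
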